### **Feasibility study**

To our knowledge studies have not examined the impact of SA interventions in genetic counseling (Etchegary & Perrier, 2007). The ClinSeq study, designed to identify health-related genetic changes through exome sequencing, examined SA related to genetic risk perception and

information seeking. Although the ClinSeq study did not include a SA intervention, surveys did include assessments of participants' tendencies to engage in spontaneous SA.

Given the lack of evidence in this context it is important to conduct a feasibility study prior to a full-scale intervention to assess genetic counselors' and clients' reactions to the SA intervention, and the logistics of and barriers to SA implementation. Feasibility research studies generally have smaller sample sizes and therefore statistically significant outcomes are not expected. These studies allow for exploration of many aspects of implementation and preliminary outcomes. The National Cancer Institute has recognized the need for more intervention-based feasibility studies prior to full-scale studies to determine "whether comprehensive and multilevel evaluations are justified (Bowen et al., 2009, p. 1)." A feasibility study of SA in genetic counseling would allow for preliminary examination of the impact of SA on genetic counseling session outcomes to provide estimates of effect size, confidence intervals and, consequently, necessary sample size for a future study.

#### **4.0 Description of study design**

This study is a randomized controlled feasibility study to assess the acceptance and initial outcomes of a self-affirmation intervention in a cancer genetic counseling context.

#### **5.0 Description of procedures:**

In this intervention-based randomized controlled feasibility study, Hereditary Breast and Ovarian Cancer (HBOC) genetic counseling clients will receive an intervention and short survey before their appointment and will complete a survey after their appointment. Genetic counselors who counsel participating clients will complete a post-appointment survey after each appointment with a participating client and a survey at the end of the study.

Thirty-five client participants will be randomly assigned to complete the self-affirmation intervention and 35 participants will complete the control condition. Client participants will be patients being seen for an initial appointment for genetic counseling at the HBOC genetic counseling clinic, regardless of current cancer status. All client participants will take a state anxiety measure before their appointment to control for some of the variability in indication. Client participants will also indicate if they have cancer, if they have received genetic testing, and if they were offered genetic testing at the current visit. Genetic counseling can be indicated for patients without cancer who have a family history of cancer, for patients with cancer, and for self-referred patients who are concerned about their cancer risk. Most often, the initial cancer genetic counseling appointment occurs before qualification for genetic testing is assessed and clients have a follow-up appointment to receive results. Sometimes oncologists or primary care physicians order genetic tests and the initial genetic counseling appointment includes results delivery and education. Any client with an initial genetic counseling appointment will be invited to participate in the study. Follow-up appointments will not be included because patients already have a relationship with the genetic counselor. The four genetic counselors, who have appointments with the participating clients, will be enrolled in the study as genetic counselor participants.

The SA intervention consists of participants ranking 11 items (artistic skills, athletics, business/money, creativity, independence, music, politics, relationships with friends and family, religious values, sense of humor, spontaneity) from most important to least important (See

[figure not shown]
Appendix C) (Creswell et al., 2013; Havranek et al., 2012). They will then be asked to write about the item that is most important to them and why it may be important to them. The control group will rank the same list and be asked to write about the 9th ranked item and why it might be important to someone else. The control condition is consistent with the control used in other SA intervention studies. The 9th ranked item is chosen to inhibit a reverse effect where participants feel affirmed because they do not value something that is aversive to them. Both the intervention and control group will receive a 6-question survey of state anxiety along with the writing prompt, which will be used as a control measure.

Potential participants will be identified through the patient schedule and will be contacted by the student assistant investigator (AI), [name], about one week prior to their appointment to invite them to participate in the study and obtain verbal informed consent. Participants will be recommended to arrive 15 minutes prior to their scheduled appointment. When clients arrive at the HBOC clinic, the front desk staff will give client participants the SA or control intervention based on random assignment. The affirmation intervention or control condition will be completed directly before the regularly scheduled appointment.

Genetic counselors will be blinded to the study condition of their clients, although clients might choose to discuss the content of the intervention survey with the counselor. Counseling sessions will otherwise proceed according to protocol for the clinic. Clients will receive a paper survey as they leave the appointment regarding their demographic information (age, sex, education, race, ethnicity, cancer status) experience in the study, decision self-efficacy, empowerment, genetic knowledge, intentions to talk with family, information seeking, and intentions to pursue genetic testing if it was offered. They will be given the option to fill out the paper version or to access an electronic version online. Hard copy surveys will be returned to the front desk or by mail to the AI. Electronic versions will be sent to an email address provided by the client. A week after their appointment, all clients will receive an electronic reminder notification to complete the questionnaire. Upon completion of the online survey or paper questionnaire participants will be mailed a \$15 gift card.

Genetic counselors at St. Luke's Health System volunteered to participate in this study and contacted the AI about their interest in participating and hosting the study. The counselors at Medstar Washington Hospital Center were contacted by the AI after initial IRB approval of this protocol in order to increase recruitment by adding an additional site.

At the onset of data collection, counselors will complete a written consent. After each appointment with a study participant, genetic counselors will complete a short client empowerment survey. After the client study is complete, genetic counselors will be given a survey about their opinions about and experience with the self-affirmation intervention. Questions will include information on their experiences and opinions about the SA. Counselors at St. Luke's Health System will each be given a \$1400 gift card at the completion of the latter questionnaire. The counselors at Medstar see fewer potential participants so their compensation will be \$200. We expect to have approximately 16 patient participants from Medstar and 54 from St. Luke's Health System. In addition, the counselors at MedStar will be involved with recruitment over a shorter period of time and will not have to expend the effort expended by the St. Luke's counselors to work through logistics prior to the study's approval

**Figure 3:** *Participants participation in protocol*

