## Protocol Summary

- Full Title:** *Is it Feasible?: Self-Affirmation for Hereditary Breast and Ovarian Cancer Genetic Counseling*
- Principal Investigator:** *[name]*
- Sample Size:** *N= 74, patient control group =35, patient treatment group = 35, genetic counselors =4*
- Accrual Ceiling:** *180 participants*
- Study Population:** *Clients being seen for an initial visit in the hereditary breast and ovarian cancer (HBOC) clinic, both affected and unaffected with cancer, female, 18-90 years-old*
- Accrual Period:** *July 2017 – February 2017*
- Study Design:** *This study is a feasibility study to assess the acceptance and initial outcomes of a self-affirmation intervention in a novel HBOC genetic counseling context. The study relies on surveys of 4 genetic counselors and 70 clients after a small case control study. The purpose is to estimate effect sizes and preliminary outcomes of self-affirmation in a genetic counseling setting and to assess client and counselor interest in self-affirmation interventions.*
- Study Duration:** Start Date: *June 2017* End Date: *March 2017*
- Primary Objective:** *To identify outcomes that may be applicable for a larger SA intervention study in the genetic counseling context by randomly assigning clients to a control or intervention arm and then surveying them after the SA intervention and genetic counseling appointment.  
To assess clients' and counselors' opinions of an SA intervention by post study surveys.*
- Secondary Objectives:** *To assess process outcomes of a SA intervention including the time required to complete the intervention, uptake, and attrition.*
- Endpoints:** *Client's completion of follow-up survey; Counselor's completion of study review survey.*

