### **Intervention (See appendix C)**

For the SA intervention, participants will be asked to rank 11 items (artistic skills, athletics, business/money, creativity, independence, music, politics, relationships with friends and family, religious values, sense of humor, spontaneity) from most important to least important (Creswell et al., 2013; Havranek et al., 2012). They will then be asked to write about the item that is most important to them and why it may be important to them. The control group will rank the same list and be asked to will write about the 9th ranked item and why it might be important to someone else. The control condition is consistent with the control used in other SA intervention studies.

Immediately after the intervention or control condition, participants will complete a 2 minute survey that consists of the short version of the Stat-Trait Anxiety Inventory (STAI). This measurement entails 6 questions to assess the client's current anxiety. The purpose of the STAI is to control for anxiety, to identify if those who are more anxious are more effected by the SA intervention. The intervention and STAI should take about 10-15 minutes together. At the end of the intervention there will be a detachable page asking for the client's email address to send them with the post-intervention survey and a reminder to complete it. This document will be immediately separated from the study material by the scheduling coordinator.

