## **7.0 Description of study statistical considerations and/or analytic plan:**

*Aims have been copied here for ease of interpretation.*

Aim 1: To assess the preliminary impact of a novel SA intervention on outcomes that may be targeted in future studies, by assessing differences in the following between a SA intervention and unaffirmed standard SA intervention control group of HBOC genetic counseling clients:

- a. Intentions to talk with family, test uptake
- b. Empowerment, decision self-efficacy
- c. HBOC knowledge

The primary goal of analysis of aim 1 is to identify which outcomes would be most appropriate for follow up studies and the necessary sample size for adequate statistical power.

For decision efficacy, the scores on the Decision Self-Efficacy Scale (See section 2 of client survey, Appendix D) will be compared between groups using linear regression controlling for education, race, anxiety score, and effectiveness of intervention (based on last question on intervention Appendix C). Intention to talk with family, genetic testing uptake, and information seeking will be measured similarly using linear regression.

Client empowerment will be analyzed by using the GCOS-24 a 24-item likert scale completed by clients and parallel scale by genetic counselors (See section 3 of client survey of appendix D and appendix F). Both scales will be compared between groups using linear regression controlling for education, race, anxiety score, and effectiveness of intervention (based on last question on survey). Discrepancies between counselor and client surveys will be analyzed using dyadic analyses. For this analysis, we will assess the correlation between paired client and genetic counselor GCOS-24 for the compete survey and for the individual questions.

HBOC knowledge will be analyzed between groups using linear regression testing the knowledge scale (See section 4 of client survey, Appendix D) and controlling for education, race, anxiety score, and effectiveness of intervention.

Effect sizes and standard deviations for each outcome will be identified, and an estimated sample size for a fully powered study will be estimated based on power calculations.

Aim 2: To describe genetic counselors' (GCs) and clients' response to a novel, client-based SA intervention, including perceived impact, barriers, and facilitators to implementing such an intervention on a wider scale

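### Education and race are collected on the take-away exit survey, so the adjusted counselor-rated empowerment model would lose clients whose counselor rating is already in hand

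*Combined protocol and SAP*

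**What the plan says.** **Exit survey.** Section 5.0 places the demographic items after the session: "Clients will receive a paper survey as they leave the appointment regarding their demographic information (age, sex, education, race, ethnicity, cancer status". The form can leave the clinic: "Hard copy surveys will be returned to the front desk or by mail to the AI". An online version is also offered, with one electronic reminder after a week.

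**Pre-visit packet.** Section 5.6 (Intervention, Appendix C) describes the ranking and writing task, the 6-item STAI and a detachable email page. Section 7.0 adds a last question that checks affirmation. The STAI is given "Immediately after the intervention or control condition". No demographic item is mentioned.

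**Counselor rating.** Section 5.0: "After each appointment with a study participant, genetic counselors will complete a short client empowerment survey". Section 5.6 identifies this as a counselor version of the GCOS-24.

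**Analysis.** Section 7.0, on the client and counselor GCOS-24: "Both scales will be compared between groups using linear regression controlling for education, race, anxiety score, and effectiveness of intervention". It gives no rule for missing covariates and no unadjusted comparison.

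**Linkage.** Under Section 10.0 a client-chosen code word goes on all of a participant's documents, including the counselor's form. Section 10.3 states that no key connects code words to clients.

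**Attrition.** The secondary objective in the Protocol Summary is: "To assess process outcomes of a SA intervention including the time required to complete the intervention, uptake, and attrition".

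**The concern.** Education and race are fixed before randomisation but are measured at the contact most exposed to loss. The counselor rating is the one Aim 1 measure that does not need the client to return anything. Adjusting it for two items held only on the exit survey gives up that advantage.

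Two things are at stake. First, the counselor comparison would shrink to returners. Return happens after randomisation, so the outcome would carry the same possible response selection as the client-reported ones. Second, the study could say how many clients were lost but not who they were by age, education, race or ethnicity. A feasibility study meant to shape a larger trial needs that description.

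**Working it through.** **1. The plan's own figure.** Section 6.1 gives 296 participants for a fully powered study with d = 0.35, alpha 0.05 and power 0.85 (the protocol labels the 0.85 as beta). The two-sided normal approximation gives n per arm = 2(1.960 + 1.036)²/0.35² = 146.6, so 147 per arm and 294 in total. The two-sample t-test gives 147.55, so 148 per arm and 296 in total. The figure reproduces and is not in dispute. The documents give no figure for exit-survey return.

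**2. What is available for a client who attends but does not return the exit survey.**

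| Term in the counselor GCOS-24 model | Where recorded, as described | Available? |
|---|---|---|
| Counselor GCOS-24 score | Counselor form, after each appointment (5.0, 5.6) | Yes |
| Arm | Random assignment, packet handed out at the front desk (5.0) | Yes |
| Anxiety (STAI) | Pre-visit packet, after the writing task (5.6) | Yes |
| Effectiveness of intervention | Last question on the intervention form; for the GCOS-24 models, Section 7.0 refers to the last question on the survey | Yes on the first reading, no if the client survey is meant |
| Education | Exit survey (5.0) | No |
| Race | Exit survey (5.0) | No |

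Ordinary regression drops a record with any covariate missing. Without a key, the chart cannot supply education or race.

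**3. Size.** Inputs: 35 clients per arm (Section 5.0) and an assumed non-return fraction f, equal in the two arms. The half-width of the 95% confidence interval for a standardised difference, without adjustment, is 1.96 × √(2/n), with n = 35(1 − f) per arm on average. The relative widening is 1/√(1 − f).

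| f (assumed) | Clients left of 70 | Ratings lost | Half-width (SD) | Widening | Half-width using t (SD) |
|---|---|---|---|---|---|
| 0 | 70 | 0 | 0.47 | – | 0.477 |
| 10% | 63 | 7 | 0.49 | 5% | 0.504 |
| 20% | 56 | 14 | 0.52 | 12% | 0.536 |
| 30% | 49 | 21 | 0.56 | 20% | 0.575 |
| 40% | 42 | 28 | 0.60 | 29% | 0.624 |

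For example, at f = 20%, n = 28 and 1.96 × √(2/28) = 0.52.

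**The case against.** **Non-returners are not blank.** A reader might infer that they have no baseline data at all. The documents do not support that. They keep the values ranking, the STAI and the affirmation item, and clinic site may be known from where the forms were collected. However, the STAI and affirmation item follow the randomised task, and none of these supplies education or race.

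**Cancer status and prior testing.** A reader might also infer that these are available only from returners. Section 5.0 lists cancer status on the exit survey, but it also says "Client participants will also indicate if they have cancer, if they have received genetic testing" without naming a form. The same sentence asks about testing offered at the current visit, which points to the exit survey but does not settle it. Neither item is a covariate in Section 7.0, so the counselor-model problem rests on education and race alone.

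**Dropping records is an assumption.** Section 7.0 does not specify a complete-case analysis. In a randomised comparison education and race serve precision, and a model without them keeps every counselor rating. This stands as a partial remedy that needs no change to the forms. It would not let attrition be described.

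**The size is hypothetical.** The 10–40% range is assumed. Return is encouraged by a $15 gift card that is forfeited on non-completion, a reminder and three ways to return the survey. The Protocol Summary can be read as meaning 70 completed client surveys, in which case the loss is not from 70; the relative widening would be unchanged. Section 3.0 does not expect significant results, and 5–12% widening at 10–20% non-return is modest.

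**Attrition profiling is not promised.** Section 7.0 commits only to a percentage for uptake. Describing who is lost is therefore an addition, though it serves the stated objective.

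**The forms are unseen.** Appendices C and D are not in the available text. If Appendix C already holds the demographic items, the protocol text is what needs correcting.

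**Conclusion.** The point holds for education and race. As the protocol describes data collection, the adjusted counselor GCOS-24 model under ordinary regression would use only clients who returned the exit survey, although the counselor ratings of the others exist. Non-returners could not be compared with returners on age, education, race or ethnicity.

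Under the assumed range, 7 to 28 of 70 ratings are lost and the half-width grows from about 0.47 SD to between 0.49 and 0.60 SD. At the roughly 8 clients a month reported for St. Luke's in Section 6.1, 7 to 28 clients represent about 0.9 to 3.5 months of that site's recruitment (7/8 and 28/8).

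The conclusion assumes that records with missing covariates are dropped, that 70 is the number randomised, that loss is equal in the two arms, and that the forms match the protocol text. It does not show that the counselor comparison would be biased: the documents give no evidence that return differs by arm or by client type. A change is worth making because it is cheap and the missing values cannot be recovered later.

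**What to change.** 1. Move the education, race, age and ethnicity items from the exit survey (Appendix D) to the end of the pre-visit form (Appendix C), after the writing task, affirmation item and STAI. The task cannot alter these facts, and last place avoids influencing it. The existing code word links them to the counselor form.
2. Treat moving cancer status and prior testing as optional. They are not covariates and would be asked just before the session. Keep the question on testing offered at the visit on the exit survey.
3. State in Section 7.0 that the counselor GCOS-24 comparison includes all randomised clients who attended, and that any affirmation item in that model comes from the pre-visit form. Whether to adjust for that item at all is a separate question.
4. For clients already enrolled without these items, also report the counselor comparison without the education and race terms.
5. Report exit-survey return by arm and by these characteristics.

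**Cost.** About one more minute before the appointment, when the intervention and STAI already take 10–15 minutes of a 15-minute early arrival; the exit survey becomes shorter. A minor amendment is needed, with the second site's review to be considered. No extra staff or visit is required. Missing values for non-returners already enrolled cannot be recovered.

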### **Responsibilities of NIH**

This study was developed by the student associate investigator, [name], for her thesis project as a part of the Genetic Counseling Training Program at the NHGRI and her thesis advisor, [name] at the NIH. Clients will be consented for participation by phone by the SI. Counselors will be consented by email or fax by the AI. The AI will distribute the study materials (intervention and surveys) to the counselors at St. Luke's Health System and Medstar Washington Hospital Center. All data will be analyzed at the NIH by the PI and AI, who are researchers from the NIH.

### **Responsibilities of St. Luke's Health System and Medstar Washington Hospital Center**

[name] and [name] are genetic counselors at St. Luke's Health System and non-NIH collaborators for this research study. The St. Luke's Health system HBOC scheduling coordinator will distribute and collect the intervention, client surveys, and contact cards on site at the St. Luke's health system HBOC clinic. The scheduling coordinator will also collect the genetic counselor after visit and end of study surveys. They will mail all deidentified materials to the NIH researchers for analysis.

[name] and [name] are the genetic counselors at Medstar Washington Hospital Center and non-NIH collaborators for this research study. Similarly to St. Luke's Health System, the front desk personnel will distribute and collect the study intervention, client surveys,

and contact cards. Because this clinic does not have one assigned clinic coordinator, the counselors will confirm and oversee that study materials are appropriately returned to the AI.

The intervention and client survey will not include identifying information and contact information will be separated from the other study materials. All surveys and the intervention are self-administered.

- 5.1 N/A
- 5.2 N/A
- 5.3 N/A
- 5.4 N/A
- 5.5 N/A
- 5.6 Describe questionnaires or other psychological instruments and estimate how long they will take to complete, and whether they address sensitive topics (Appendix C-F)

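### At Medstar the counselors, who are meant to be blinded, oversee the return of forms that show the arm, and nothing requires their empowerment rating to come first

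*Combined protocol and SAP*

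**What the plan says.** The blinding statement is in section 5.0, Description of procedures: "Genetic counselors will be blinded to the study condition of their clients, although clients might choose to discuss the content of the intervention survey". Client disclosure is the only leak that it acknowledges.

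Three statements describe who handles the forms:

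- **Handing out (section 5.0).** On arrival, "the front desk staff will give client participants the SA or control intervention based on random assignment".
- **Supply (Responsibilities of NIH).** "The AI will distribute the study materials (intervention and surveys) to the counselors at St. Luke's Health System and Medstar Washington Hospital Center".
- **On-site handling (site responsibilities).** At St. Luke's, the "scheduling coordinator will distribute and collect the intervention, client surveys, and contact cards on site", collects the counselor surveys, and mails the materials to the NIH. At Medstar, front-desk personnel distribute and collect, but there is no single coordinator, so "the counselors will confirm and oversee that study materials are appropriately returned to the AI".

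The two forms differ in what the client writes about. One asks for an essay on the top-ranked value, the other for an essay on the ninth-ranked value and why someone else might care about it (sections 5.0 and 5.6). Under section 10.0 the client's code word goes on every document for that client, and the client gives it to the counselor in the session so that the after-visit survey can be labeled.

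That survey is the counselor version of the GCOS-24, 24 Likert items on how empowered the counselor perceives the client to be. Section 7.0 uses it under Aim 1 alongside the client version: "Both scales will be compared between groups using linear regression". It also correlates the paired client and counselor scores.

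**The concern.** Blinding matters most for an outcome that is a rater's impression, and the counselor GCOS-24 is one. At Medstar the rater is also assigned oversight of the documents that reveal the arm. Removing names does not protect the blind, because the code word lets the counselor tie a form to a client she has just seen. The form is filled in directly before the appointment, so it is already on site when the rating is made.

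Aim 1 exists to choose outcomes for a later study and to set its sample size. A counselor-rated effect inflated by knowledge of the arm could make this outcome look more responsive than it is, and could make the next study too small. Section 10.0 keeps counselor identity off the after-visit surveys, so bias by individual counselor could not be examined afterward. Clinic site is recorded, so a comparison by site would be possible.

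**Working it through.** **Step 1. Can the Medstar counselor learn the arm from the role assigned to her?**

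| Link in the chain | Where stated | Stated or inferred |
|---|---|---|
| Returned materials include the completed form | Site responsibilities, section 5.0 | Stated: the intervention is among the items collected |
| The form shows the arm | Sections 5.0 and 5.6 | Follows from the two prompts |
| The form can be tied to a client | Section 10.0 | Stated: code word on all documents and told to the counselor |
| The counselor sees the form's content | Site responsibilities | Not stated; overseeing return makes it possible |
| Contact comes before the rating | Section 5.0 | Not stated; the rating follows each appointment, with no order relative to the forms |

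The first three links are in the text. The last two are left open. The body of the protocol describes no sealed envelopes, no concealment of completed forms from counselors, no rating-first rule and no check of blinding. The appendices were not part of the text reviewed.

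**Step 2. Inputs.** Expected clients: 16 at Medstar and 54 at St. Luke's, total 70 (section 5.0). Allocation: 35 per arm (section 5.0). Planning effect for a future full study: d = 0.35, total 296, 0.85 and 0.05 (section 6.1). The documents give no size for a rating bias, so b = 0.2 to 0.5 SD is an assumption.

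**Step 3. The plan's own figure.** With d = 0.35, two-sided alpha 0.05 and power 0.85 (section 6.1 labels the 0.85 as beta, but the figure reproduces as power), a two-sample t-test needs 147.55 per arm. This rounds to 148, or 296 in total, as stated. The normal approximation gives 147 per arm, 294 in total. The figure is not in dispute.

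**Step 4. Shift in the pooled difference.** Suppose every Medstar rating is made knowing the arm, the arms are balanced within site, and the bias favors the intervention. Then shift = b × 16/70.

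- Medstar share: 16/70 = 0.229.
- b = 0.2: 0.2 × 0.229 = 0.046 SD.
- b = 0.3: 0.3 × 0.229 = 0.069 SD.
- b = 0.5: 0.5 × 0.229 = 0.114 SD.

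**Step 5. Compare with sampling error.** The unadjusted standard error at 35 per arm is √(2/35) = 0.239 SD, with a 95% half-width of 1.96 × 0.239 = 0.47 SD. The shift is 0.046/0.239 = 0.19 to 0.114/0.239 = 0.48 standard errors. With no true effect, the two-sided 5% error rate would rise to 5.4% to 7.7%.

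**Step 6. Carry-over into planning.** Suppose the true counselor-rated effect were 0.35 and the inflated value were used directly to size the next study (normal approximation, power 0.85).

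| b (assumed) | Planning d | Total N | Power at true d = 0.35 |
|---|---|---|---|
| 0 | 0.35 | 294 | 85% |
| 0.2 | 0.35 + 0.046 = 0.396 | 230 | 76% |
| 0.5 | 0.35 + 0.114 = 0.464 | 168 | 62% |

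**The case against.** The best defense is that the Medstar role is administrative. Front-desk personnel still hand out and collect the forms. Overseeing return may mean only checking that packets went out, and the rating may already be done by then. The study is a feasibility study that does not expect significant results, the outcome is one of several, and the illustrated shift is well below one standard error. All of this is fair. It limits the likely size of the bias and rules out saying that blinding fails. It does not supply the missing safeguard: the plan assigns a task in tension with its own blinding statement and sets no order between that task and the rating.

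Two stronger readings are tempting, and the documents support neither.

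- **That counselors at both sites are unblinded because study materials are sent to them.** Supplying forms to a site does not tell a counselor which version a given client received. At St. Luke's (54 of 70 clients) the coordinator hands out, collects and mails the forms, and nothing puts a completed form in a counselor's hands. Supply to counselors is a weaker, secondary route, worth closing but not a basis for applying the whole assumed shift to all 70 clients.
- **That client-reported outcomes are biased as well.** That would require the counselor to know the arm before or during the session. Overseeing return does not imply this, and clients complete their own surveys, on paper or online.

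**Conclusion.** The concern holds for Medstar. A role that the plan assigns conflicts with the blinding that it states, and no described step resolves the conflict. What is exposed is the counselor GCOS-24 comparison and the client-counselor correlation, for about 23% of clients. The pooled shift is about 0.05 to 0.11 SD, against a standard error of about 0.24 SD.

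That range rests on an assumed shift of 0.2 to 0.5 SD and on all 16 Medstar ratings being made with knowledge of the arm, so it is an illustration and not an estimate. If the forms are never seen before the rating, the bias from this route is zero. The change is still worth making, because it is nearly free and the bias could not be removed afterward.

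**What to change.** 1. **Rating first.** Require the counselor GCOS-24 to be completed and handed in before the counselor has any contact with that client's study materials.
2. **Sealed completed forms.** Have front-desk staff detach the email page, as section 5.6 needs someone to do at once, and then place the completed form in a sealed opaque envelope. Medstar counselors check only the count of sealed envelopes.
3. **Supply route.** Amend Responsibilities of NIH so that the associate investigator sends the intervention and control forms, in sealed numbered packets, to the front desk or scheduling coordinator and not to the counselors.

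The cost is envelopes and one paragraph of procedure. Sample size, staffing and the analysis model do not change.
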